9.4.2. Primary Endpoint(s)

Study MTAE has a 76-week common close design wherein all enrolled participants continue on study drug and complete study assessments until last enrolled participant that has not discontinued reaches 76 weeks of double-blind treatment. The maximum duration of treatment is 124 weeks.

The primary objective of this study is to test the hypothesis that LY3372689 slows cognitive and functional decline in early symptomatic AD participants with moderate cortical tau burden as measured by iADRS compared with placebo through end time point (76-124 weeks). This will be assessed using DPM as the primary analysis, and MMRM analysis will be performed as a sensitivity analysis.

The iADRS score at each scheduled postbaseline visit (according to the SoA) during the treatment period will be the dependent variable. The DPM is as follows:

$$Y_{ij} = \gamma_i + e^{\theta_{T_i}} \sum_{v=0}^j \alpha_v + \varepsilon_{ij}, i = 1, 2, \dots, k; j = 1, 2, \dots, l$$

where Y_{ij} denotes the clinical outcome at visit j for participant i , clinical outcome scores at baseline (prior to treatment) is Y_{i0} . T_i denotes the treatment arm for participant i . The parameter γ_i ($i=1, 2, \dots, k$) represents the subject-specific random effect for participant i . e^{θ_T} is the disease progression ratio (DPR) for treatment T and $e^{\theta_T} = 1$ for placebo; e^{θ_1} and e^{θ_2} represent the DPR of the low dose and the high dose, respectively. The parameter α_v is the mean change of placebo response from visit $v-1$ to v . ε_{ij} is the error term. Any stratification variables used for randomization such as investigator site and prior or current use of any approved disease-modifying therapy for AD will be included in the model. Baseline score, baseline age, concomitant acetylcholinesterase inhibitor (AChEI)/memantine use (yes/no) will be included in the model as well. Diffuse priors will be used for the Bayesian inferences in the DPM analysis. A DPR less than 1 corresponds to a slowing of disease progression; similarly, a DPR greater than 1 reflects some evidence of cognitive worsening. The DPM will be fitted to the data and Bayesian inferences will be summarized including posterior distribution of DPR and posterior probabilities of various DPR thresholds of interest (e.g., 0.75 which translates to 25% slowing of disease progression with LY3372689 group versus placebo). The null hypothesis is that the DPR between the LY3372689 group versus placebo equals 1.

The primary endpoint will also be assessed using natural cubic spline model with degrees of freedom 2 (NCS2) and MMRM to serve as sensitivity analyses. Additional models/analyses may be considered if deemed appropriate. The SAP will describe the planned analyses in greater details.

9.4.3. Secondary Endpoint(s)

The key secondary objective of this study is to test the hypothesis that LY3372689 slows cognitive and functional decline in early symptomatic AD participants in the overall population as measured by iADRS compared with placebo through end time point (76-124 weeks). It will be analyzed using the NCS2, MMRM and the Bayesian DPM as described in Section 9.4.2, with the adjustment for tau burden (moderate versus high) as defined by flortaucipir PET.

Other secondary efficacy outcomes include ADAS-Cog₁₃, ADCS-iADL, CDR-SB, and MMSE. Each of these 4 secondary efficacy endpoints will be assessed using the same analysis method(s) applied to the primary endpoint iADRS and will be analyzed for both moderate tau sub-population and the overall population. The change from baseline score at each scheduled

postbaseline visit (according to the SoA) during the treatment period will be analyzed using the NCS2. Greater details of model specifications will be provided in the SAP.

The change from baseline to Week 76 in tau deposition (as measured by flortaucipir F18 PET scan) will be analyzed using an ANCOVA model with terms of baseline value and treatment.

Longitudinal change in vMRI parameters up to Week 76 will be analyzed using MMRM including the following terms in the model: treatment, visit, treatment-by-visit interaction, baseline vMRI, and intracranial volume. Other baseline covariates may be included.

For data beyond Week 76, including flortaucipir F18 PET and MRI, MMRM may be used to analyze the data with terms of baseline value and treatment.

An additional analyses of secondary efficacy and biomarkers endpoints may be performed and will be pre-specified in the SAP.

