A database lock is expected to occur after all randomized participants have had a chance to complete their final study visit in the double-blind period of the study (study period 2a/2b). Efficacy and safety analyses will be conducted based on data collected during the double-blind period. Data collected during post-treatment safety follow-up period (study period 3) will be summarized and analyzed separately.

Additional database lock(s) may occur during the post-treatment safety follow-up period (study period 4). Efficacy and safety analyses will be conducted based on data collected during the double-blind and/or post-treatment safety follow-up period.

Any change to the data analysis methods described in the protocol will require an amendment only if it changes a principal feature of the protocol. Any other change to the data analysis methods described in the protocol, and the justification for making the change, will be described in the SAP and the CSR. Additional exploratory analyses of the data will be conducted as deemed appropriate.

The study will include 2 SAPs: a main study SAP (referred to as Study SAP) which will detail the analyses for the objectives for double-blinded, placebo-controlled phase, and post-treatment safety follow-up period; a supplemental SAP which will detail the additional exploratory analyses using data collected from post-treatment safety follow-up period.

The main Study SAP will be finalized prior to unblinding of all participants in the placebo-controlled phase, and it will include a more technical and detailed description of the statistical analyses described in this section. This section is a summary of the planned statistical analyses of the most important endpoints including primary and key secondary endpoints.

Handling of missing, unused, and spurious data is addressed prospectively in the overall statistical methods described in the protocol and in the SAPs, where appropriate.

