- Probability (at least 25 % slowing of disease progression on iADRS in LY3372689 high dose relative to placebo) > probability threshold 1.
- Probability (at least 25 % slowing of disease progression on iADRS LY3372689 low dose relative to placebo) > probability threshold 2.

These two thresholds will be calculated after unblinding at PODBL to establish the accurate probability thresholds that correspond to each alpha level as shown in graphical testing scheme above. As the thresholds can be sensitive to the underlying assumptions of placebo trajectory and the variance-covariance matrix, the methodological approach to find the probability thresholds is pre-specified below. The established thresholds will be documented in the CSR.

1. The NCS2 results for the iADRS (Section 4.8.2.1) from the moderate tau population will provide the underlying assumptions that are needed for this simulation. The following will be utilized: the LS mean placebo trajectory and the number of participants with data from the placebo arm at each visit; the pooled variance covariance matrix as estimated from the NCS2.
2. To create a null distribution, simulate multivariate normal data for the number of participants from the moderate tau population representing the placebo arm, assuming all participants have the same decline as the placebo arm from the NCS model and the same variability. The amount of data simulated for each treatment arm will reflect the exact number of participants at each visit from the placebo arm.
3. The posterior probability of at least 25% slowing is calculated by fitting the Bayesian DPM to each 100,000 simulated dataset. The Bayesian DPM as described in Section 4.8.1 but without covariate adjustment. The threshold is the lowest value at which at least $(\alpha/2 \times 100)\%$ of the simulated posterior probabilities are larger. Note that the probability threshold 2 will be re-calculated if it makes all the way down to tau imaging biomarker in the high dose arm.

The tests for the rest of the graph: CDR-SB, iADL, and ADAS-Cog13 will be based on the p-value of the difference of averaged LSM change across Week 64 to Week 88 between the treatment arms; tau imaging biomarker endpoint AD-signature VOI will be based on the p-value of the difference of LSM change at Week 76 between the treatment arms.

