4.9.3. Other Secondary Endpoints Analyses

4.9.3.1. Analysis of Volumetric MRI

Analyses of the following volumetric MRI (vMRI) parameters will be conducted (right + left for all but whole brain volume and ventricular volume):

- Hippocampal volume (mm³)
- Atrophy of total whole brain volume (cm³)
- Enlargement of Ventricular volume (cm³)

To evaluate the changes in vMRI parameters, an MMRM model will be used to compare change from baseline to Week 76 between the treatment arms in the Efficacy Evaluable analysis set within moderate tau population and full study population, respectively.

The change from baseline at each post-baseline visit up to Week 76 will be the dependent variable. The model will include the fixed effects of treatment, visit as a categorical variable, treatment-by-visit interaction, and adjusted for baseline vMRI value and age at baseline. Baseline tau PET category will also be included as a fixed effect to the model when analyzing full study population. The null hypothesis is that the difference in LS mean between both the active treatment arm and placebo equal zero. Analyses including post-Week 76 visits may be included for exploratory purpose.

To assess the relationship of vMRI with efficacy endpoints up to Week 76, Spearman's rank correlation coefficient may be obtained on baseline and change from baseline on vMRI parameters versus change from baseline for iADRS, CDSR-SB, ADAS-Cog13, ADCS-ADL, and MMSE. This will be performed using participants who have both the clinical outcome and vMRI result at Week 52 and Week 76, respectively. This analysis may be performed in moderate tau subpopulation and/or the full study population. The correlation analysis including post-Week 76 timepoints such as Week 100 and Week 124 may be conducted for exploratory purpose.

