4.14. Changes to Protocol-Planned Analyses

No changes to the planned protocol analyses have been made.

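### SAP 4.9.3.1 drops the intracranial volume term that Protocol 9.4.3 specifies for the volumetric MRI model, while SAP 4.14 declares no change

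*Protocol*

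**What the plan says.** Protocol 9.4.3 specifies an MMRM for change in vMRI parameters up to Week 76. After treatment and visit, its fixed list of terms ends with "treatment-by-visit interaction, baseline vMRI, and intracranial volume". The next sentence leaves room for more: "Other baseline covariates may be included".

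SAP 4.9.3.1 applies an MMRM to hippocampal volume (mm³), whole brain volume (cm³) and ventricular volume (cm³). On the outcome it says: "The change from baseline at each post-baseline visit up to Week 76 will be the dependent variable". The terms are arm, visit and their interaction, "adjusted for baseline vMRI value and age at baseline", with baseline tau PET category added in the full study population. Intracranial volume does not appear, and no head-size normalisation of the volumes is described.

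SAP 4.14 says: "No changes to the planned protocol analyses have been made". Protocol 9.4.1 lets analysis methods change without an amendment unless a principal feature is affected, on condition that the change, and "the justification for making the change, will be described in the SAP and the CSR".

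**The concern.** The protocol makes intracranial volume a listed term and leaves only further covariates optional. The SAP omits the listed term, gives no reason and states that nothing has changed.

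Two things are at stake.

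- **Pre-specification.** Brain volume is a stated secondary objective and appears in SAP Section 2 among the hypotheses for important secondary objectives. With two different models on record, there is room to choose between them after seeing results.
- **Head size.** The volumes are analysed in absolute units. As general reasoning, not drawn from the documents, baseline regional volume may reflect both head size and atrophy that has already happened. These could push later absolute loss in opposite directions, and a single baseline coefficient cannot represent both. An explicit intracranial volume term could separate them and might tighten the treatment contrast.

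**Working it through.** **1. Model terms side by side**

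| Term | Protocol 9.4.3 | SAP 4.9.3.1 |
|---|---|---|
| Arm, visit, arm-by-visit | yes | yes |
| Baseline vMRI value | yes | yes |
| Intracranial volume | yes, listed | absent |
| Age at baseline | allowed as an optional covariate | yes |
| Baseline tau PET category | allowed as an optional covariate | yes, full population only |

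The one departure is the missing intracranial volume term.

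**2. Is it declared anywhere?** SAP 4.14 declares nothing. The SAP version history for Version 3 records only that Sections 4.9.2 to 4.9.3 gained detail. The protocol text does not look like a leftover: the amendment history shows that Section 9.4.3 was revised in amendment (c), 22 March 2024, to match the latest plan for secondary endpoints. The SAP names protocol (d), 18 April 2024, as its basis.

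**3. Size of the precision effect.** The documents give no vMRI standard deviation, effect size, power or intracranial volume correlation, so there is no stated figure to reproduce. Let r be the partial correlation of intracranial volume with volume change, given the other terms. Then:

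- SE with the term / SE without it = √(1 − r²)
- share of sample size that the term is worth = r²

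| Assumed r | √(1 − r²) | Fall in SE when restored | Sample-size equivalent |
|---|---|---|---|
| 0 | 1.000 | 0% | 0% |
| 0.1 | √0.99 = 0.995 | 0.5% | 1% |
| 0.2 | √0.96 = 0.980 | 2.0% | 4% |
| 0.3 | √0.91 = 0.954 | 4.6% | 9% |

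**4. In terms of power (illustration).** Take about 80 completers per arm (Protocol 9.2, whole trial), two-sided alpha 0.05, and an effect set to give 80% power with the term. The standardised effect is (1.960 + 0.842) × √(2/80) = 0.443. Without the term the SE is multiplied by 1/√(1 − r²) = 1, 1.005, 1.021 and 1.048, and power is 80.0%, 79.6%, 78.4% and 76.2%.

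**5. Simulation check.** This was a two-arm ANCOVA at a single time point, 80 per arm, 1,000 replicates per scenario. The assumed correlation of intracranial volume with baseline volume ran from 0.3 to 0.9, and the assumed direct standardised effect of intracranial volume on change from 0 to 0.3.

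- The SE ratio (without the term / with it) ran from 0.997 to 1.037.
- With no direct effect, including the term cost about 0.3% in SE.
- With the largest direct effect, omitting it cost 3.7% when the correlation was 0.3, but only 0.6% when it was 0.9, because baseline volume then carries most of the head-size information.
- The mean estimated treatment difference stayed near its true value of zero in both models.

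**6. Where vMRI sits in the testing plan.** After iADRS, SAP 4.9.2.1 lists the remaining nodes: "The tests for the rest of the graph: CDR-SB, iADL, and ADAS-Cog13 will be based on the p-value", followed by the tau PET endpoint. vMRI is not named.

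**The case against.** The strongest reply is that little depends on this. The outcome is within-participant change and the model adjusts for each participant's own baseline volume, so head size is partly accounted for. Randomisation protects the treatment contrast from bias with or without the term. vMRI is outside the named gated tests and no success criterion in the SAP uses it. All of this stands.

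Three further objections also carry weight.

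- A reader might infer that the SAP traded intracranial volume for age and that adding age is itself a departure. It is not, because Protocol 9.4.3 permits further covariates.
- No section says that intracranial volume was derived. SAP 4.9.3.1 names only three volumes. Protocol 8.2.5 has a central vendor calculate brain volumes, and a screening MRI is scheduled, so availability is a reasonable assumption and no more.
- SAP Version 5 is dated 20 June 2025 and the documents give no unblinding date. If the double-blind data had already been unblinded, adding a covariate now would itself need disclosure.

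None of this removes the mismatch between Protocol 9.4.3 and SAP 4.9.3.1, or makes the statement in SAP 4.14 correct. Protocol 9.4.1 allows the SAP to depart from the protocol's method, but only with a description and a justification, and neither is given.

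**Conclusion.** The point holds as an undeclared departure from the protocol with a small statistical consequence. The SAP omits a covariate that the protocol lists and states that nothing changed; this follows from the texts alone and needs no assumption.

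The precision effect does rest on assumptions. It runs from nothing to a fall in SE of 4.6% for assumed partial correlations from 0 to 0.3, and r need not be the same for hippocampus, whole brain and ventricles.

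Two stronger readings are tempting and the documents do not support them. One is that head size is left unadjusted: change scores and baseline volume adjust for it in part, and what is missing is the explicit term. The other is that the analysis definitely loses precision: no correlation or variance is given, and r = 0, where nothing is lost, cannot be excluded.

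The primary result is not affected. The follow-up MMRM in SAP 4.15.3 also has no intracranial volume term, but the protocol's list concerns change up to Week 76, so that is not a second departure.

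**What to change.** Add baseline intracranial volume, assumed derivable from the screening MRI, as a covariate in the SAP 4.9.3.1 MMRM for hippocampal, whole-brain and ventricular volume, and keep age. The SAP then runs the protocol's model and the statement in 4.14 becomes true on this point.

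If the term was left out deliberately, or the double-blind data are already unblinded, state and justify the departure in SAP 4.14 and in the CSR, and report the protocol-specified model alongside the SAP model.

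The cost is one extra parameter per model and, if intracranial volume has no direct effect on change, about 0.3% in SE. No further scan is needed if the assumption about the screening MRI holds; that should be confirmed with the central imaging vendor.

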9.4.4. Tertiary/Exploratory Endpoint(s)

Exploratory endpoints and their respective analyses will be described in the SAP.

9.4.5. Treatment Group Comparability

9.4.5.1. Participant Disposition

All participants who discontinue from the study will be identified, and the extent of their participation in the study will be reported. If known, a reason for their discontinuation will be given.

The reasons for discontinuation will be collected when the participant's participation in the study ends and will be summarized by treatment group for all randomized participants. The percentage of participants discontinuing from each treatment group will be compared between groups using Fisher's exact test. The comparisons will be done for the overall percentage of participants who discontinue and for select specific reasons for discontinuation.

9.4.5.2. Participant Characteristics

The participant's age, sex, race, height, body weight, body mass index (weight (kg)/[height (m)]²), tobacco use, alcohol use, caffeine use, years of education, work status, marital status, time since onset of first AD symptoms, time since diagnosis, baseline MMSE, ApoE genotype (e.g., E4 carrier versus non-carrier), having 1 or more first degree relatives with AD, and use of approved prescription AD medications will be recorded.

Baseline characteristics will be summarized by treatment group, primary efficacy subpopulation, and overall population. Summaries will include descriptive statistics for continuous and categorical measures. Fisher's exact test or Pearson's chi-square test will be used for treatment-group comparisons of categorical data. For continuous data, analysis of variance (ANOVA), with independent factors for treatment and investigator, will be used.

9.4.5.3. Prior and Concomitant Therapy

Prior medications are defined as those that stop before randomization (Visit 2). Concomitant medications are defined as those being taken on or after randomization (Visit 2). A summary of

concomitant medications will be presented as frequencies and percentages for each treatment group. Fisher's exact test will be used to test for treatment differences between groups.

If the start or stop dates of therapies are missing or partial to the degree that determination cannot be made of whether the therapy is prior or concomitant, the therapy will be deemed concomitant.

Prior and concomitant medications will be listed.

Summary tables will also be provided for concomitant anticholinergics that affect cognitive function and use of approved prescription AD medications.

Medications will be coded using the World Health Organization drug dictionary.

9.4.5.4. Treatment Compliance

The proportion of participants who are significantly noncompliant as described in Section 6.4 of this protocol will be summarized and compared among all treatment groups using Fisher's exact test.

9.4.6. Safety Analyses(s)

All safety analyses will be made on the Safety Population. Refer to the SAP for additional details.

9.4.7. Other Analyses

9.4.7.1. Pharmacokinetic/Pharmacodynamic Analyses

LY3372689 plasma concentrations will be illustrated graphically and summarized descriptively.

If warranted and based on availability of data, the exposure-response relationship of LY3372689 concentrations to biomarkers, pharmacodynamic endpoints, efficacy endpoints, and/or safety endpoints may be explored. Data from other clinical studies evaluating LY3372689 may be combined with data from this study to support exposure-response analyses. Such analyses may be reported separately.

9.4.7.2. Analysis of C-SSRS Data

Suicide-related thoughts and behaviors occurring during treatment will be summarized based on responses to the C-SSRS consistent with the C-SSRS Scoring and Data Analysis Guide (CUIMC 2016).

9.5. Interim Analyses

Interim analyses may be conducted for Study MTAE; for example, when 50% of randomized participants have had a chance to complete 52 weeks of treatment (Visit 15), data may be used to evaluate whether to stop the study for futility. Operational details and a quantitative framework to provide information for these decisions will be documented in the SAP.

Only the DMC is authorized to evaluate unblinded interim efficacy and safety analyses. Study sites will receive information about interim results only if they need to know for the safety of trial participants.

Unblinding details are specified in the unblinding plan section of the SAP or in a separate unblinding plan document.

The timing of dissemination of data summaries based on interim analyses is addressed in Section [10.1.6](#).

9.6. Data Monitoring Committee

For details on DMC, refer to Appendix [10.1.5](#)

10. Supporting Documentation and Operational Considerations

10.1. Appendix 1: Regulatory, Ethical, and Study Oversight Considerations

10.1.1. Regulatory and Ethical Considerations

- This study will be conducted in accordance with the protocol and with the following:
 - consensus ethical principles derived from international guidelines including the Declaration of Helsinki and Council for International Organizations of Medical Sciences (CIOMS) International Ethical Guidelines
 - applicable ICH GCP Guidelines,
 - regulation (EU) No. 536/2014, if applicable, and
 - other applicable laws and regulations.
- The protocol, protocol amendments, ICF, IB, and other relevant documents (e.g., advertisements) must be submitted to an IRB/IEC by the investigator and reviewed and approved by the IRB/IEC before the study is initiated.
- Any amendments to the protocol will require IRB/IEC approval before implementation of changes made to the study design, except for changes necessary to eliminate an immediate hazard to study participants.
- The investigator will be responsible for the following:
 - providing written summaries of the status of the study to the IRB/IEC annually or more frequently in accordance with the requirements, policies, and procedures established by the IRB/IEC
 - notifying the IRB/IEC of SAEs or other significant safety findings as required by IRB/IEC procedures,
 - providing oversight of the conduct of the study at the site and adherence to requirements of 21 Code of Federal Regulations (CFR), ICH guidelines, the IRB/IEC, European regulation 536/2014 for clinical studies (if applicable), and all other applicable local regulations.
 - reporting to the sponsor or designee significant issues related to participant safety, participant rights, or data integrity.
- Investigator sites are compensated for participation in the study as detailed in the CTA.

